1. AMENDMENTS FROM PREVIOUS VERSION(S)

NA. First version.

2. LIST OF ABBREVIATIONS

Abbreviation	Definition
aHR	Adjusted hazard ratio
CDC	Centers for Disease Control and Prevention
CI	Confidence interval
СРТ	Current Procedural Terminology®
CVX	Clinical Vaccines Administered code
EUA	Emergency use authorization
FDA	U.S. Food and Drug Administration
HV	HealthVerity
ICD-10-CM	International Classification of Diseases, Tenth Revision, Clinical Modification
ICU	Intensive care unit
NDC	National Drug Codes
RSV	Respiratory syncytial virus
SAP	Statistical Analysis Plan
SMD	Standardized mean differences
NPI	National provider identifier
VE	Vaccine effectiveness

Note: in this document, any text taken directly from the non-interventional (NI) study protocol is *italicized*.

3. RATIONALE AND BACKGROUND

Until recently, vaccine registries were not available for de-identification and linkage to secondary claims-based databases. However, through a collaboration with HealthVerity, a leading supplier of secondary health data, the State of California and the State of Louisiana have made their vaccine registries available for linkage for research purposes. California and Louisiana deidentify the registries, using HealthVerity's software to convert each patient's protected health information to a unique HealthVerity ID which can then be linked to the full HealthVerity database to gather clinical history and outcomes.

The purpose of this document is to detail the statistical methods and analyses that will be used in the HealthVerity claims database linked to the State of California/Louisiana's vaccine registries to address Aim 1 of the study protocol. Separate SAPs will be produced to address the other aims of the protocol.

4. STUDY OBJECTIVES AND HYPOTHESES

The objective of Aim 1 of this study is to evaluate the vaccine effectiveness (VE) of BNT162b2 formulations in non-pregnant, non-immunocompromised adults against medically attended COVID-19, mortality and healthcare resource utilization by age and adapted vaccine formulation.

This study is descriptive in nature and as such does not include any pre-specified hypotheses.

5. RESEARCH METHODS

5.1. Study Design

This will be a retrospective cohort study using data from patients who were California or Louisiana residents in the HealthVerity claims database.

Cohort identification will begin from the date of Emergency Use Authorization (EUA) or U.S. Food and Drug Administration (FDA) approval for the BNT162b2 formulation. Study follow-up will occur from FDA EUA or approval date until COVID-19 diagnosis or other outcome of interest (hospitalization, emergency department visit, outpatient encounter, end of medical and/or pharmacy enrollment, or death [according to the mortality database]).

The authorization/approval dates for each BNT162b2 formulation that will be used in this study are provided in Table 5.1. Note that EUA (for children age 6 months to 11 years) and approval (age 12+) status for the bivalent vaccine was revoked on the date the XBB.1.5 formulation became available.

Table 5.1 Timeline of Key BNT162b2 Regulatory Milestones Applicable to Non-immunocompromised Adults

Vaccine formulation	Age group	Event
BNT162b2 monovalent	Age 12 and	September 11, 2023: U.S. Food and Drug
XBB.1.5 COVID-19 vaccine	older	Administration (FDA) approval
BNT162b2 bivalent BA.4/5	Age 12 and	August 31, 2022: FDA EUA
COVID-19 vaccine	older	-

All persons will be considered unvaccinated from date of FDA date of vaccine authorization/approval until, where applicable, 13 days after receipt of vaccine. In order to allow for time after dose for meaningful immunologic protection to accrue, persons will be considered vaccinated 14 days after vaccination.

The full data available, from December 1, 2018, will be used as the look-back period to define patient's characteristics, clinical history, risk factors, and healthcare utilization.

The outcomes of interest are medically attended COVID-19, mortality and healthcare resource utilization and are described in Table 5.2.

Main summary measure: VE = (1 - adjusted hazard ratio [aHR]) * 100, comparing vaccinated to unvaccinated persons during the same time period.

5.2. Study Population

Patients who were California or Louisiana residents in the HealthVerity claims database will be defined using the following hierarchical definition:

- 1. Persons who have their enrollment file record indicating a patient location of California or Louisiana in HealthVerity claims enrollment file.
- 2. Persons who have a patient state location other than California or Louisiana in HealthVerity claims enrollment but have one or more records in the California or Louisiana Immunization Registry. Examples include people who previously lived in Texas but moved to California and received a vaccine, or persons who crossed state lines for a vaccine and remain in their non-California state in claims data.

Patients who meet the following criteria will be included in the analysis:

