Inclusion criteria in trials generally reflected age-related eligibility for vaccination.	For brevity, we will not discuss each of the 5 aim's different inclusion criteria here. Throughout, we used age at time vaccine was authorized or approved by FDA for time-varying exposures, age at vaccination for time-fixed exposures to reflect age-related eligibility.			
	We require continuous pharmacy and medical enrollment in HealthVerity prior to index date (FDA EUA date per vaccine) for follow-up. This is in order to establish pre-existing health status, which would have been queried at study entry in the clinical trials.			
	We require continuous California/Louisiana residency to maximize pre-index capture of vaccines, as people living outside of California /Louisiana would not have prior vaccines well captured in the registry.			
	Throughout, we will exclude people who are currently pregnant, using a validated			

- Exclusion criteria
 - Pregnant
 - Treatment with immunosuppressive therapy or diagnosis with an immunocompromising condition
 - History of COVID-19

gestational age algorithm with up to 9 months lookback. 18

Except in aim 4, where the analyses are specific to immunocompromised persons, we will exclude immunocompromised people considering claims for medications dispensed as well as and diagnosis codes.

We will exclude persons with a diagnosis of COVID-19 in any setting ≤ 90 days prior to index. We are limiting to 90 days as reinfections have become more common over the pandemic and were rare during the Fall 2020 clinical trial period. We believe 90 days represents a reasonable period in which persons then can be considered to be at risk for reinfection, and also are eligible for vaccination. ¹⁹

We will exclude individuals with discrepancies in sex and/or year of birth between HealthVerity claims and California/Louisiana immunization registry datasets, as these are key confounders in all analyses. Secondary deidentified data makes it impossible to reconcile differences, which would be expected to be resolved with primary data collection.

Treatment strategies

Receive 1 dose of a BNT162b2 adapted formulation vs. no BNT162b2 formulation or other COVID-19 vaccine (XBB.1.5 or BA.4/5 depending on timing)

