5.2. Study Population

Patients who were California or Louisiana residents in the HealthVerity claims database will be defined using the following hierarchical definition:

- Persons who have their enrollment file record indicating a patient location of California or Louisiana in HealthVerity claims enrollment file.
- 2. Persons who have a patient state location other than California or Louisiana in HealthVerity claims enrollment but have one or more records in the California or Louisiana Immunization Registry. Examples include people who previously lived in Texas but moved to California and received a vaccine, or persons who crossed state lines for a vaccine and remain in their non-California state in claims data.

Patients who meet the following criteria will be included in the analysis:

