5.2.1. Inclusion Criteria

- 1. Born in 2005 or earlier (as age 18 or older in 2023, owing to the data providing year but not month or day of birth).
- 2. At least one year of pharmacy and medical enrollment in HealthVerity prior to index date (FDA approval/EUA date per vaccine). A gap of up to 30 days will be allowed.

3. Have been a State of California/Louisiana resident for at least one year prior to index date (FDA approval/EUA date per vaccine). A gap of up to 30 days will be allowed.

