5.3.3. Covariates

The list of demographic and clinical characteristics that will be used to describe the cohort and considered for inclusion as covariates in models are provided in Table 5.3. Age, sex, state of residence and prior COVID-19 vaccinations will be obtained from the HealthVerity claims database and state vaccine registries. The HealthVerity claims database will be the sole source of all other variables.

All covariates will be assessed on or prior to index date and will therefore be considered as time-fixed variables during the follow-up. Categories may be collapsed or covariates may be excluded or combined if models fail to converge or if patient counts are low (Section 5.7.2). Additionally, categories with large patient counts may be split further.

Table 5.3 Demographic and Clinical Characteristics

Variable	Role(s)	Operational definition
Age	-Inclusion/ exclusion	Age assessed at index date.
	criteria	Categorized as: 18-49, 50-64 or 65+ years.
	-Descriptive	
	(continuous and	
	categorical)	
	-Covariate	
	(categorical)	
	-Subgroup	
	(categorical)	
Sex	-Inclusion/ exclusion	Sex assessed at index date.
	criteria	Male, female or unknown.
	-Descriptive	
	-Covariate	
State of residence	-Inclusion/ exclusion	Defined in Section 5.2
	criteria	California or Louisiana
	-Descriptive	
	-Covariate	
	-Subgroup	
Payor	-Descriptive	Payor assessed at index date.
	-Covariate	Commercial, Medicaid, Medicare Advantage,
		Unknown, Missing

Variable	Role(s)	Operational definition
CDC-defined high	-Descriptive (any	Assessed in the year prior to index
risk for severe	high-risk condition	• Age ≥ 50 years
COVID-19 ²	and for each	Asthma
	individual condition)	Cancer, as hematologic malignancies
	-Covariate (each	Cerebrovascular disease
	individual condition except age ≥ 50 years)	Chronic kidney disease: people receiving dialysis
		Chronic lung diseases: bronchiectasis,
		COPD, interstitial lung disease, pulmonary
		embolism, pulmonary hypertensionChronic liver diseases: cirrhosis, non-
		alcoholic fatty liver disease, alcoholic liver
		disease, autoimmune hepatitis
		Cystic fibrosis
		Diabetes mellitus, type 1
		Diabetes mellitus, type 2
		Disabilities, including Down syndrome
		Heart conditions: heart failure, coronary
		artery disease, or cardiomyopathiesHIV
		Mental health conditions: mood disorders
		including depression; Schizophrenia
		spectrum disorders
		Neurologic conditions limited to dementia
		Obesity (BMI ≥30 kg/m²)
		Primary immunodeficiencies

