5.4.1. California and Louisiana Immunization Registries

The California Immunization Registry is run by the California Department of Public Health and collects nearly all records of COVID-19 vaccinations administered in the state of California.

Data include a unique HealthVerity person identification code, vaccination event date and Clinical Vaccines Administered (CVX) code. CVX codes are unique to brand and formulation of vaccine.

Data is linked using HealthVerity's tokenization software, whereby specific patient identifiers are passed through the software and a de-identified patient ID is assigned. The same tokenization process is applied to closed claims sourced by HealthVerity, and patients can thus be linked across data sources. The tokenization process occurs outside of Pfizer, no personal identifying information will be transferred, and Pfizer will only have access to de-identified data. The data comply with Health Insurance Portability and Accountability Act (HIPAA) regulations.

The Louisiana Vaccine Registry is structured and accessed in the same way as California.

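### Residency rule 2 admits out-of-state enrollees only through a vaccination record that need not precede index, so entry for this group can depend on future exposure

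*SAP*

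**What the plan says.** Aim 1 SAP section 5.2 defines California/Louisiana (CA/LA) residents in two tiers. Rule 1 is a CA/LA location in the claims enrollment file. Rule 2 adds people whose claims location is another state "but have one or more records in the California or Louisiana Immunization Registry". One example given is people who moved to California. The other is "persons who crossed state lines for a vaccine and remain in their non-California state in claims data". No date is attached to the record. Protocol 8.2 and 8.4.2, the Aim 2 SAP (5.2) and the Aim 3B SAP (5.2.1) carry the same rule.

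Aim 1 SAP 5.4.1 says that the California registry "collects nearly all records of COVID-19 vaccinations administered in the state of California", and that Louisiana's is built the same way. A record is therefore a COVID-19 vaccination.

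On top of this, Aim 1 SAP 5.2.1 requires the person to "Have been a State of California/Louisiana resident for at least one year prior to index date", with a gap of up to 30 days. Aim 2 requires six months. In Table 5.3 of the Aim 1 SAP, state of residence is simply "Defined in Section 5.2". The protocol's reason for the residency requirement (Table 2) is that "people living outside of California /Louisiana would not have prior vaccines well captured in the registry".

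**The concern.** In the target trial the plan emulates, eligibility is settled at time zero, here 11 September 2023. Rule 2 lets it be settled later. Of two otherwise identical out-of-state enrollees, the one with a CA/LA vaccination can enter and the one without cannot, and nothing says the vaccination must come before index. Where the only record is the post-index XBB.1.5 dose, the exposure itself opens the door. That person's earlier unvaccinated time is then conditional on later vaccination.

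The never-vaccinated contrast is the most exposed. An out-of-state enrollee with no pre-index dose on record can reach it only through a post-index registry dose.

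Rule 2 also admits the group for whom the protocol itself says prior doses are poorly captured. The analysis would not show the effect. State is coded only as California or Louisiana, the sensitivity analyses named in Aim 1 SAP 5.7.7 do not address the rule, and protocol 8.9 does not list it as a limitation.

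**Working it through.** **1. Who can enter.** Taking the rule, the one-year criterion and the follow-up definition (Aim 1 SAP 5.2, 5.2.1, 5.7.3) together, for an enrollee with an out-of-state claims address:

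| CA/LA registry history | Enters? | Contributes |
|---|---|---|
| None, ever | No | Nothing |
| Older dose, no XBB.1.5 dose | Yes, subject to the one-year criterion | XBB-unvaccinated time, but not in the never-vaccinated stratum |
| Older dose, then BNT162b2 XBB.1.5 | Yes, subject to the same | Unvaccinated, then vaccinated time |
| Only the post-index BNT162b2 XBB.1.5 dose | Literal reading yes; strict reading of one-year residency no | Unvaccinated time to 13 days after the dose, then vaccinated time |

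The documents do not settle the last row. Residence refers back to section 5.2, and no text says how a rule-2 person shows a year of it.

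**2. The plan's own figures (Aim 1 SAP 5.5).**
- Doses: 0.75 × 12,000,000 × 0.16 × 0.60 = 864,000. Reproduced.
- Adults at start: 0.95 × 9,000,000 = 8,550,000. Reproduced.
- Table 5.4, VE 30% at 1,000 cases per 100,000: CI 28 to 32, a half-width of (32 − 28)/2 = 2 points.

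**3. Possible share of exposed persons (assumed inputs).** Suppose rule-2 entrants are 0.5% to 2% of 9,000,000 adults, that is 45,000 to 180,000.
- If half enter only through the XBB.1.5 dose: 22,500/864,000 = 2.6% to 90,000/864,000 = 10.4%.
- If they resemble the claims population (63% with at least one dose, protocol 8.5; expected uptake 16% × 60% = 9.6%), and every XBB.1.5 recipient were a first-time vaccinee: 9.6/(63 + 9.6) = 13.2%. The shares become 0.7% to 2.8%.

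The documents support neither the 0.5–2% nor the half. Doses received elsewhere could push the 13.2% up.

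**4. Effect on VE (illustration).** Inputs from the plan: 8,550,000 adults, 9.6% vaccinated (820,800), uniform vaccination from day 14, 5% censoring, 1,000 cases per 100,000, true VE 30%. Follow-up is taken as 182 days, with vaccinated status starting 14 days after the dose. Let f be the assumed share of vaccinated persons who enter only through a post-index dose, so f × 820,800/(1 − f) are added. They are taken as event-free until vaccinated status starts. Let c be their assumed event rate, or event capture, relative to other vaccinated persons. Solving the expected Cox score equation gives estimated VE (%):

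| f | Added persons | c = 1 | c = 0.5 | c = 0 |
|---|---|---|---|---|
| 1% | 8,291 | 29.97 | 30.32 | 30.67 |
| 5% | 43,200 | 29.85 | 31.61 | 33.36 |
| 10% | 91,200 | 29.69 | 33.20 | 36.72 |
| 20% | 205,200 | 29.30 | 36.37 | 43.44 |

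Hand check, ignoring pre-dose time: VE ≈ 1 − 0.70 × [(1 − f) + f·c]. For f = 5%, c = 0.5: 1 − 0.70 × 0.975 = 31.75%, against 31.61%. For f = 10%, c = 0: 1 − 0.70 × 0.90 = 37.0%, against 36.72%. The gap is the effect of event-free pre-dose time.

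The c = 1 column isolates that time: 30 − 29.30 = 0.7 points downward at f = 20%. This is an upper limit for that mechanism. A person can have COVID-19 first and be vaccinated later, and rule 2 would still admit them.

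**5. Never-vaccinated stratum.** With 100 − 63 = 37% having no recorded dose (an all-age figure, applied here to adults) and an assumed 1% uptake: 0.37 × 8,550,000 × 0.01 = 31,635 vaccinated. A 10% share then needs only 31,635 × 0.10/0.90 = 3,515 entrants. VE would be 29.97%, 33.47% and 36.97% for c = 1, 0.5 and 0.

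**The case against.** The strongest reply is that section 5.2 only defines the source population and the one-year criterion applies on top of it. A 30-day gap allowance makes sense only for dated residency spans, so a person whose sole CA/LA evidence is a post-index dose would fail. This is a fair reading, and a reader who concludes that rule 2 defeats the criterion outright goes beyond the text. But the text does not establish the reply either. Residence is defined by the undated rule, and the cross-state example describes people who never became residents.

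Three other inferences are tempting and not supported:
- *That rule-2 entrants have no unexposed counterparts.* Those with older registry doses who skip XBB.1.5 do supply unvaccinated time. The lack of persistently unvaccinated comparators is confined to the never-vaccinated contrast.
- *That rule-2 people are generally misfiled as never vaccinated.* Anyone whose registry record predates index cannot be. The risk applies to those whose only record is post-index and whose doses elsewhere are unseen.
- *That VE is inflated by a known amount.* The shares in step 3 are assumptions, and event-free pre-dose time pulls VE down slightly. An upward shift needs c below 1. Protocol 8.2 derives endpoints from claims restricted to the two states, which could drop out-of-state encounters. Protocol 8.4.3, however, expects claims to capture nearly all encounters.

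For Aim 3B the objection largely succeeds. The comparison is COVID-19 against control and vaccination is a stratifier, so the rule affects only the vaccination strata.

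**Conclusion.** The concern stands in limited form. Followed literally, rule 2 lets entry for out-of-state enrollees depend on a vaccination after index, and the one-year criterion may or may not prevent it. The weak point is clearest in the never-vaccinated contrast of Aims 1 and 2. Rule-2 people with older doses are less of a problem as comparators, but their doses given elsewhere are poorly captured, against the protocol's own reason for requiring residency.

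Size and direction are unknown because the documents do not count these entrants. Under the illustration's assumptions, event-free pre-dose time costs at most 0.7 VE points for shares up to 20%. Fewer or missed events would add 1.6 points at f = 5%, c = 0.5, and 6.7 points at f = 10%, c = 0. Against a CI half-width of about 2 points at 1,000 cases per 100,000, the large sample would not hide the bigger shifts. The change should be made, because the rule can select on exposure and the remedy is cheap. The documents do not show that the estimates are materially wrong.

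**What to change.** For Aims 1 and 2, define residency in the primary analysis by the claims enrollment address over the required pre-index period: one year for Aim 1, six months for Aim 2. Align protocol 8.2 and 8.4.2 with this. Section 8.4.2 uses the most recent enrollment record, which need not describe the pre-index period.

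If rule 2 is kept:
- accept only registry evidence dated before index that satisfies the residency period, and never a post-index dose;
- state how that period is shown for a rule-2 person;
- report the number of rule-2 entrants by exposure, overall and in each prior-vaccination subgroup;
- report results for rule-1 residents only.

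Requiring the record to predate the look-back would not work. The look-back opens on 1 December 2018, before the first authorization on 11 December 2020, so no COVID-19 vaccination could qualify.

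For Aim 3B, a note that the rule can affect the vaccination strata is enough.

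No new data are needed. The cost is a somewhat smaller cohort and the loss of some genuine movers whose claims address is out of date.

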5.2.1. Inclusion Criteria

- 1. Born in 2005 or earlier (as age 18 or older in 2023, owing to the data providing year but not month or day of birth).
- 2. At least one year of pharmacy and medical enrollment in HealthVerity prior to index date (FDA approval/EUA date per vaccine). A gap of up to 30 days will be allowed.

3. Have been a State of California/Louisiana resident for at least one year prior to index date (FDA approval/EUA date per vaccine). A gap of up to 30 days will be allowed.

5.2.2. Exclusion Criteria

- 1. Currently pregnant (using 9 months lookback with a codelist for current pregnancy)¹ or immunocompromised (using 1 year lookback) at the time of study index (definitions are provided in the Protocol Annex)
- 2. Individuals with discrepancies in sex and/or year of birth between HealthVerity claims and California/Louisiana immunization registry datasets. In cases where sex or year of birth is unknown in either the claims or dataset but available in the other, individuals will be included and the information from the dataset where year of birth or sex is available will be used, regardless of whether the information stemmed for claims or registry data.
- 3. Persons with a diagnosis of COVID-19 (ICD-10-CM U07.1) in any setting \leq 90 days prior to index (FDA approval/EUA date per vaccine)
- 4. Receipt of COVID-19 vaccine \leq 60 days prior to index (FDA approval/EUA date per vaccine).

5.2.3. Subgroups and Stratification

Results will be stratified by age group (overall, age 18-49, 50-64, 65+).

Additionally, the analysis of the primary outcome will be stratified by state of residence. As tests and measures of heterogeneity can be affected by large sample sizes, clinical relevance will be used to assess the difference in VE estimates between the two registries. If a difference is deemed clinically relevant, secondary and exploratory outcomes may be additionally stratified by state of residence.

The following subgroups will be used to evaluate relative VE for the XBB.1.5 vaccine:

- Prior receipt of BA.4/5 bivalent vaccine
- Receipt of two prior doses of mRNA COVID-19 vaccine and no prior receipt of BA.4/5 bivalent vaccine
- No prior receipt of any COVID-19 vaccine

